3.3 Vulnerable patient populations

Pregnant women are considered a vulnerable population. As the condition of interest is a pregnancy-related and specific condition, it is unavoidable to exclude pregnant women from this research study. However, propranolol is currently used in clinical practice in pregnant women for other medical indications, so the risks to this population are minimally increased from that experienced in routine clinical care.

Furthermore, neonates are considered a vulnerable population. We will be collecting data on neonates for our composite neonatal outcome. All risks to this vulnerable population will be minimal risk. Propranolol is a medication that is used clinically in the neonatal population for management of retinopathy of prematurity and hemangiomas. Neonatal risks of this study include the risk of neonatal hypoglycemia, respiratory depression, and bradycardia. Neonatal blood glucose screening is routine at HUP for all neonates whose mothers receive a β blocker intrapartum. Neonatal hypoglycemia is a rare but known side effect of intrapartum β blocker use. This occurs most commonly for women who receive labetalol intrapartum for blood pressure control. In one large study of over 2 million neonates, the rate of neonatal hypoglycemia was found to be 4.3% among those exposed to intrapartum β blockers, compared to 1.2% among controls. After adjusting for confounders, the odds ratio of neonatal hypoglycemia was found to be 1.68 [95% CI 1.50-1.89].⁹ National guidelines do not specify maternal use of β blockers as an indication for routine blood glucose monitoring in asymptomatic infants, but this is standard of care at UPHS, so all neonates included in this study will undergo routine hypoglycemia via heel stick at 3 time points within the first 24 hours of life. There are many risk factors for neonatal hypoglycemia and it is possible that these neonates would have required a glucose check regardless of enrolling in the study. In general, approximately 30% of all neonates born at term at UPHS meet criteria for glucose screening. The only additional risks to the neonate include chart review after delivery. Subjects will be made aware of these risks and that we will be collecting information on their neonates within the consent form.

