2.2.2 Secondary Endpoints

- Time (hours) from start of labor/IOL to delivery

- Time (hours) from study drug administration to delivery
- Time (hours) from start of second stage of labor to delivery
- Indication for CD
- Operative vaginal delivery
- Cumulative and maximum dose of intrapartum oxytocin received
- Postpartum hemorrhage
- Maternal blood transfusion
- Endometritis
- Chorioamnionitis
- Wound infection
- Other composite maternal morbidity: VTE, Hysterectomy, ICU admission, Maternal readmission within 7 days and 4 weeks, Maternal death
- ICN adm > 48 hours
- Composite neonatal outcome: neonatal blood transfusion, HIE, IVH grade 3 or 4, head cooling, severe RDS, NEC, Sepsis, Death

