3.2 Exclusion Criteria

Severe preeclampsia: as patients will be receiving magnesium and possibly labetalol for hypertension control

Receiving other beta blocker

Maternal heart rate < 70 beats per minute, systolic blood pressure <90 mmHg, or diastolic blood pressure <50 mmHg on two sets of vital signs in the 1 hour prior to study drug administration: given that bradycardia and hypotension are possible side effects of propranolol

History of any form of asthma: as this is a contraindication to beta blocker use

Diabetes requiring insulin in labor: given the potential risk of neonatal hypoglycemia in the neonate

Any cardiac condition for which β blockade is contraindicated (cardiogenic shock, sinus bradycardia, and greater than first degree heart block)

Known hypersensitivity to propranolol

Intrauterine fetal demise since different labor protocols are used in these women

Major fetal congenital anomaly since rate of cesarean may be inherently different in these women, unrelated to labor

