4.5 Duration of Follow Up

Women/neonate dyads will be followed for the development of any maternal or neonatal complications through the duration of the postpartum hospital stay as well as for readmissions within 30 days of delivery.

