5.6 Protections Against Physical Risk

There is minimal risk to the use of propranolol during labor. This medication is currently employed in clinical use in pregnant women, and other β -blocking medications such as labetalol are commonly used in laboring women in the University of Pennsylvania Health System. A DSMB comprised of individuals who are not investigators on the trial will be utilized to monitor for adverse outcomes. A list of mandatory events that should be reported to the DSMB within 24 hours of occurrence will be supplied to all clinicians and research coordinators managing trial patients. Also all serious adverse events will be recorded and reported to the institutional review board.

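### Neonatal hypoglycemia is a stated drug risk and is checked in every neonate, but no by-arm report of it is planned; separately, Sections 6.2.1 and 6.2.3 disagree on readmission

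*Combined protocol and SAP*

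**What the plan says.** **Neonatal hypoglycemia.** Section 3.3 says: "Neonatal risks of this study include the risk of neonatal hypoglycemia, respiratory depression, and bradycardia". It calls hypoglycemia a rare but known effect of intrapartum beta-blockade. It cites a large cohort with rates of 4.3% in exposed neonates and 1.2% in controls, and an adjusted odds ratio of 1.68 (95% CI 1.50 to 1.89). It then commits that "all neonates included in this study will undergo routine hypoglycemia via heel stick at 3 time points within the first 24 hours of life". Section 3.2 excludes women who need insulin in labor, "given the potential risk of neonatal hypoglycemia in the neonate".

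The purpose given in 3.3 for neonatal data is narrower: "We will be collecting data on neonates for our composite neonatal outcome". Section 2.2.2 defines that outcome as "Composite neonatal outcome: neonatal blood transfusion, HIE, IVH grade 3 or 4, head cooling, severe RDS, NEC, Sepsis, Death". The only other neonatal endpoint is an intensive care nursery stay above 48 hours. The adverse event list in 6.2.1 names maternal hypoglycemia only, and the neonatal list in 6.2.3 has no glucose item. Section 8.2 gives generic between-group tests and names no safety outcome.

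**Readmission.** Section 2.2.2 includes "Maternal readmission within 7 days and 4 weeks" in a maternal composite. Section 6.2.1 lists readmission to 7 days as an adverse event. Section 6.2.3 makes in-patient hospitalization, or its prolongation, a criterion for seriousness, with a 24-hour threshold. It then says that the events meeting the criteria are those it lists, and readmission is not among them.

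**The concern.** The protocol treats neonatal hypoglycemia as important enough to exclude a group of women, to disclose to participants and to test for in every neonate, but it sets up no named comparison. The cited evidence is observational, and its crude association shrinks markedly on adjustment. Glucose measured on one schedule in both arms of a blinded randomized trial would be free of that confounding. Without a named outcome, the neonatal composite could look balanced while this known risk goes unreported by arm. If someone tabulates it later, the case definition and format would be chosen after the data exist. Neonatal bradycardia, named in the same sentence of 3.3, is also missing from the endpoint and event lists.

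The readmission conflict affects speed and route of reporting. A serious event reaches the principal investigator within 24 hours whatever its attribution (6.4.1). An event that is only an adverse event may wait for the annual report (6.4.2).

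**Working it through.** **1. Arm size.** Section 8.1 gives cesarean rates of 45% and 30%, 80% power and alpha 0.05; 8.2 makes tests two-tailed. With pooled variance under the null and 1:1 allocation (the documents state no ratio):

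n = [1.960 × √(2 × 0.375 × 0.625) + 0.842 × √(0.45 × 0.55 + 0.30 × 0.70)]² / 0.15² = 162.3, so 163 per arm and 326 in total.

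The plan's own figure reproduces and is not disputed. Pregnancies are singleton, so there are 163 neonates per arm.

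**2. Crude against adjusted association.** Crude OR = (0.043/0.957) / (0.012/0.988) = 3.70, against the adjusted 1.68 in 3.3.

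**3. What a by-arm report would show.** For control rate p0 and odds ratio 1.68, p1 = 1.68·p0 / (1 − p0 + 1.68·p0). Expected cases are 163 × rate. RD = p1 − p0, and its Wald 95% CI is RD ± 1.96 × √[(p0(1 − p0) + p1(1 − p1))/163]. Power is by exact enumeration of both binomials, two-sided 0.05. The 1.2% and 4.3% rates come from 3.3; the 5% and 10% control rates are illustrative.

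| Scenario | p0 | p1 | Cases, placebo | Cases, propranolol | RD, points (95% CI) | Power, chi-square | Power, Fisher |
|---|---|---|---|---|---|---|---|
| Cited control rate, OR 1.68 | 1.2% | 2.00% | 1.96 | 3.26 | 0.80 (−1.92 to 3.52) | 7.8% | 2.1% |
| Cited crude rates | 1.2% | 4.3% | 1.96 | 7.01 | 3.10 (−0.43 to 6.63) | 39.0% | 26.6% |
| Illustrative, OR 1.68 | 5% | 8.12% | 8.15 | 13.24 | 3.12 (−2.24 to 8.49) | 20.0% | 14.6% |
| Illustrative, OR 1.68 | 10% | 15.73% | 16.30 | 25.64 | 5.73 (−1.51 to 12.97) | 34.1% | 28.3% |

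Worked example, first row: p1 = 1.68 × 0.012 / (0.988 + 0.02016) = 0.0200, and 163 × 0.0200 = 3.26. The Wald interval is only a rough guide with so few cases.

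**4. What would still be captured.** Section 4.5 has dyads "followed for the development of any maternal or neonatal complications", and 9.2 collects unspecified neonatal outcomes to discharge. A long nursery stay would pick up some cases indirectly. The general adverse event definition includes abnormal laboratory findings, but in a patient receiving study treatment, which does not clearly include the neonate. The catch-all in 6.2.3 covers only unexpected events that the principal investigator attributes to the intervention. None of these produces a named by-arm comparison.

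**5. Readmission, section by section.**

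- 6.2.3, general criterion: the 24-hour threshold may apply to prolongation only, or to hospitalization as well. A readmission of 24 hours or more is serious on either reading; a shorter one is serious on one reading only.
- 6.2.3, list: readmission is absent, so by the list it is not a serious adverse event.
- 6.2.1: readmission within 7 days is an adverse event.
- 6.2.3, other clauses: the catch-all needs an unexpected event attributed to the intervention, and the important-medical-event clause is discretionary. Neither settles how other readmissions are classified.

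**The case against.** The strongest reply is that silence is not a plan to withhold. Nothing forbids a by-arm table, complications are followed, and 8.2 supplies tests for any categorical variable. Section 8.2 names no outcome at all, so its silence on safety is weak evidence. This is fair as to wording: the gap is the lack of a named, prespecified comparison. It does not close the gap.

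Second, 5.6 refers to "A list of mandatory events that should be reported to the DSMB within 24 hours of occurrence", and 9.4.1 to a DSMB attachment. Neither is in the supplied text, and either may cover part of this. That stands as a limit. It bears mainly on the adverse event half, since a reporting list would not by itself create an outcome compared by arm.

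Third, the heel sticks are described as standard care, and the protocol does not say the values enter the study database. This also stands: the values would have to be abstracted from charts for about 326 neonates, and the documents give no glucose threshold.

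Fourth, the cited rates describe intrapartum beta-blockers as a class, and 3.3 says the effect is seen most often with labetalol. Applying them to this propranolol regimen is an extrapolation.

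Fifth, power is poor and every interval in the table includes zero. That rules out a confirmatory test, not a descriptive count of a disclosed harm.

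Finally, the readmission point is unrelated to glucose, and readmissions are not lost: they are an endpoint to 4 weeks and are followed to 30 days. What remains there is the classification, timing and route of reporting.

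**Conclusion.** Both points hold. The plan names neonatal hypoglycemia as a risk and has it measured in every study neonate, but provides for no by-arm result. At the cited rates the trial would see about 2 placebo cases against 3.3 to 7.0 on propranolol; at illustrative control rates of 5% and 10%, 8.2 against 13.2 and 16.3 against 25.6. Across these cases power is 8% to 39% by chi-square and 2% to 28% by Fisher's test, so the report would be descriptive.

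The figures rest on 1:1 allocation, complete glucose data, the transfer of class-level cohort figures to this regimen, and an uncertain control rate. Testing every neonate could raise that rate; excluding insulin-requiring diabetes could lower it.

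On readmission, the general definition and the list in 6.2.3 give different answers for a readmission of 24 hours or more, and the documents do not settle which governs.

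This is a change that should be made, not one on which the trial's main conclusion depends. Confidence is medium because the mandatory-event list and the DSMB attachment could not be read.

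**What to change.** 1. Add neonatal hypoglycemia to 2.2.2 as a descriptive secondary safety outcome and to 6.2.1 as a listed adverse event. Base it on the three glucose values already measured, and write the sites' existing threshold into the protocol before unblinding, after confirming that both hospitals use the same one. In 8.2, state that it is reported by arm as counts and a risk difference with 95% CI, without a claim of power. An interval method suited to small counts would be preferable to Wald. Tabulate neonatal bradycardia as charted, if feasible.

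2. Reconcile 6.2.1 with 6.2.3. One way is to state that the general seriousness definition overrides the list, so that readmissions meeting it are reported as serious adverse events. State also whether the 24-hour threshold applies to hospitalization as well as to prolongation.

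3. If the mandatory-event list in 5.6 already covers these events, cross-refer to it instead.

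**Cost.** Protocol wording, a few data fields and chart abstraction of up to three values per neonate; no new procedures and no change to the sample size. Expect some more SAE forms. Bradycardia, if included, needs its own definition and abstraction.

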3.4 Ensuring Necessary Medical Interventions

Enrollment in this study will not alter any aspects of routine labor management. Continuous EFM and tocometry will occur on all patients in labor, consistent with standard of care. The remainder of clinical care in labor will be at the covering OB providers' discretion. The frequency and timing of cervical examinations will occur per provider discretion. Standard treatment for GBS positive and GBS unknown patients will occur. The use of internal fetal monitoring and intrauterine pressure catheter will be at the discretion of the OB provider. Standard obstetric indications for cesarean delivery will be also be at the discretion of the OB provider. There will be no additional blood draws or cervical examinations for women enrolled in this study.

3.5 Potential Benefit to Participants

The potential benefit will be reduced risk of CD among individuals randomized to the intervention arm. This will lead to a possible reduction in maternal and neonatal morbidity associated with unscheduled CD. Additionally, the results of this study will benefit future patients in labor. All efforts will be taken to minimize the risks associated with this study and the risks overall are considered minimal; therefore, the risk to subjects is reasonable compared to the benefit to patients and to society in general.

4 TREATMENT ARMS

4.1 Treatment Dosage and Administration

- Propranolol hydrochloride 2mg IV
 - One possible repeat dose of 2mg IV given ≥ 2 hours later if < 2 cm cervical dilation change over > 2 hours on subsequent exam
- Placebo – 2mL of 1% normal saline solution IV
 - One possible repeat dose of 2mL IV given ≥ 2 hours later if < 2 cm cervical dilation change over > 2 hours on subsequent exam

4.2 Toxicities

Any patient who receives treatment will be evaluated for toxicity. Each patient will be assessed for the development of toxicity according to vital sign monitoring or symptoms. In the event of developing bradycardia, hypotension, heart block, cardiogenic shock, bronchospasm, anaphylaxis, or signs of an allergic reaction, the second dose will not be administered.

4.3 Concomitant Medications/Treatments

All participants will be already receiving oxytocin for labor augmentation prior to receiving the study medication. No additional labor augmentation agents will be utilized. No additional β -blocker, antihypertensive, or vasoactive medications will be utilized in conjunction with the study medication.

4.4 Duration of Therapy

All participants are eligible for a maximum of one repeat dose of the study medication, until they reach 10cm dilation or decision is made to proceed with cesarean delivery, whichever comes first. After this point, they will not be eligible for any further study medication.

4.5 Duration of Follow Up

Women/neonate dyads will be followed for the development of any maternal or neonatal complications through the duration of the postpartum hospital stay as well as for readmissions within 30 days of delivery.

4.6 Removal of patients from protocol therapy

Patients will be removed from therapy when any of the criteria listed in Section 4.2 and 5.5 apply. The Principal Investigator will be notified and document the reason for study removal

and the date the patient was removed in the Case Report Form. The patient will be followed-up per protocol.

4.7 Blinding

This is a double blind study and therefore physicians, staff, and patients will be blinded to the patient's allocated treatment group. In the event of a potential suspected unexpected serious adverse reaction, unblinding will be undertaken by the PI. Unblinding may also be performed at the request of a senior clinician responsible for the care of a trial participant but such requests are likely to occur only in the case of an adverse clinical event and are expected to be rare. Any request to unblind treatment allocation for clinical reasons will be made directly to IDS and the treatment allocation will be reported to the relevant clinician. The PI and main trial manager will be kept informed of all instances of unblinding but remain blind to treatment allocations themselves wherever possible. All requests for unblinding will be recorded by research staff and IDS.

5 STUDY PROCEDURES

5.1 Screening for Recruitment and Recruitment Process

Women meeting the criteria listed in section 3.1 will be invited to participate in the study and written informed consent will be obtained from those who choose to participate. The screening procedures include:

- Informed Consent
- Medical history: Complete medical and surgical history
- Demographics: Age, gender, race, ethnicity
- Review subject eligibility criteria
- Review previous and concomitant medications
- Physical exam including vital signs, height and weight
- Vital signs (temperature, pulse, respirations, blood pressure), height, weight
- Adverse event assessment: Baseline adverse events will be assessed. See section 6 for Adverse Event monitoring and reporting.

5.2 Randomization

Eligible, consented women will receive pre-randomized study medication. Study medications will be prepared and randomized by the Investigational Drug Service (IDS) via a random generated randomization scheme. The randomization scheme will be generated by a pharmacy associate within IDS not involved in the clinical care of the patient. Two single-use vials of the same medication – either propranolol or placebo- will be included in a numbered bag. One vial will be used for the first dose. If a patient meets eligibility criteria to receive a repeat dose, the second vial in the same bag will be used.

5.3 Procedures During Treatment

After study enrollment, the covering clinician will place an EPIC order for "investigational study drug" and will retrieve the next available pre-randomized study medication bag that will be available in the labor floor medication room. The number labeling the study medication bag will be recorded by the clinician and the patient's identification label will be applied to the used vial of study medication after administration and returned to IDS for confirmation and record keeping. The time of administration of the study drug will be recorded by the patient's nurse in EPIC. For a repeat dose of medication, the RN will use the second vial of medication

included in the same study medication packet, record the administration of the dose in EPIC, and label and return the medication to IDS in the same manner.

Patients in both groups will undergo similar vital sign monitoring before and after each dose of study medication. Patients will have routine vital sign monitoring every 15-30 minutes depending on the stage of labor (including heart rate, blood pressure, and oxygen saturation assessment) through the duration of their enrollment in the study.

The remainder of clinical care in labor and delivery will occur as per primary OB provider's discretion as described in section 3.4.

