The dose regimen in our proposal (2mg IV followed by up to one repeat dose \geq 2 hours later) is based on previous clinical trials of propranolol used in labor, as well as current accepted practice and propranolol dosing regimens used in other clinical scenarios. We believe that IV is more appropriate than PO in this context as the onset of action and half-life of the IV formulation is shorter than PO and more appropriate for the time frame of intended effect. According to the propranolol package insert, the usual dose is 1 to 3 mg, and the rate of administration should not exceed 1 mg per minute to diminish the possibility of lowering blood pressure. According to the labeling, a second dose may be given after two minutes. Our proposed protocol will be compliant with this recommendation.

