6.2 Definitions

6.2.1 Definition of Adverse Event

An adverse event (AE) is any untoward medical occurrence in a patient receiving study treatment and which does not necessarily have a causal relationship with this treatment. An AE can therefore be any unfavorable and unintended sign (including an abnormal laboratory finding), symptom, or disease temporally associated with the use of an experimental intervention, whether or not related to the intervention.

For the purposes of this study, the following will be considered an adverse event:

- Maternal bradycardia < 50 beats per minute within 30 minutes of drug administration
- Maternal hypotension <80/40 mmHg within 30 minutes of drug administration
- Maternal bronchospasm
- Maternal hypoglycemia requiring treatment
- Maternal allergic reaction
- Chorioamnionitis
- Endometritis
- VTE
- Blood transfusion
- Readmission within 7 days
- NICU admission > 48 hours

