7 DRUG/DEVICE INFORMATION

7.1 Propranolol hydrochloride

- Other names for the drug: Inderal
- Classification - type of agent: β -blocker, antiarrhythmic
- Mode of action: Propranolol is a nonselective beta-adrenergic receptor blocking agent that specifically competes with beta-adrenergic receptor stimulating agents for available receptor sites, thereby decreasing chronotropic, inotropic, and vasodilator responses to beta-adrenergic stimulation.
- Protocol dose: 2mg IV; one possible repeat dose \geq 2 hours later
- Route of administration for this study: IV push
- Incompatibilities: there are no medications that are contraindicated for use with propranolol
- Availability: commercially available, on formulary
- Side effects: hypotension, congestive heart failure, bradycardia, heart block, cardiac arrest, bronchospasm, and cutaneous ulcers. (Please refer to the manufacturer's package insert for a complete list of adverse events)
- Nursing implications: Propranolol is excreted in breast milk.

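### Post-dose vital signs have no set minutes, so brief, symptom-free bradycardia or hypotension may go uncounted in the 30-minute adverse-event window

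*Combined protocol and SAP*

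**What the plan says.** - **Monitoring (protocol 5.3).** The dose-related requirement is "Patients in both groups will undergo similar vital sign monitoring before and after each dose of study medication". No minute or number of readings follows. The only stated frequency is "Patients will have routine vital sign monitoring every 15-30 minutes depending on the stage of labor", covering heart rate, blood pressure and oxygen saturation.
- **Events to be counted (6.2.1).** The list includes "Maternal bradycardia < 50 beats per minute within 30 minutes of drug administration" and "Maternal hypotension <80/40 mmHg within 30 minutes of drug administration".
- **How toxicity is found (4.2).** "Each patient will be assessed for the development of toxicity according to vital sign monitoring or symptoms". Bradycardia or hypotension found this way stops the second dose.
- **Dosing (4.1, 7.1, 1.2).** "Route of administration for this study: IV push". A second 2 mg dose is possible at least 2 hours after the first. Section 1.2 reports from the package insert that "the rate of administration should not exceed 1 mg per minute to diminish the possibility of lowering blood pressure".
- **Other monitoring (3.4).** The only continuous monitoring named is fetal and uterine. No other section sets a post-dose time for maternal readings.

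**The concern.** The protocol defines two adverse events by their timing relative to the dose, but it does not time the measurement that would detect them. The routine cycle follows stage of labor, so its readings fall at arbitrary minutes relative to the injection. The one reading tied to the dose has no minute attached.

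Timing matters because the drug is pushed intravenously. Section 1.2 links lower blood pressure to the rate of injection, which points to the first minutes after the dose. Under 4.2, a fall without symptoms is found only if a reading coincides with it.

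What is at stake is the completeness of two safety counts. Section 8 lists a rise in event frequency among the findings that could prompt a safety review, and 5.6 has a DSMB watching for adverse outcomes. Missed events lower the absolute rates in both arms and make a true difference harder to see.

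**Working it through.** The plan gives no number of readings and no detection rate, so it has no figure of its own to reproduce on this point. The 326 women in 8.1 are used below only to cost the fix. That figure does reproduce: 45% versus 30%, 80% power, two-sided 0.05, pooled variance, no continuity correction and 1:1 allocation (assumed) give 163 per arm, or 326.

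**Inputs from the protocol.** Routine interval I = 15 to 30 minutes (5.3); window of 30 minutes (6.2.1); at least 120 minutes between doses (4.1).

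**Assumptions, none of them in the documents.** Fall length d of 5 or 10 minutes. Onset uniform over 0-15 minutes after the dose, with results for 0-20 minutes in brackets. Routine cycle at random phase relative to the dose. Any post-dose check is separate from the cycle. No symptoms.

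**Step 1. Routine readings in the window.** 30/15 = 2 and 30/30 = 1. The untimed check may add one.

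**Step 2. Routine cycle alone.** P = min(1, d/I).
- d = 10: 10/30 = 33%; 10/15 = 67%.
- d = 5: 5/30 = 17%; 5/15 = 33%.

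**Step 3. Add one check at a random minute of the window.** P = 1 - (1 - d/I)(1 - d/30).
- d = 10: 1 - (2/3)(2/3) = 56%; 1 - (1/3)(2/3) = 78%.
- d = 5: 1 - (5/6)(5/6) = 31%; 1 - (2/3)(5/6) = 44%.

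**Step 4. Put that check at minute 10 instead, d = 10.** It records onsets from 0 to 10, which is 10/15 (10/20) of them.
- I = 30: 1 - (2/3)(1/3) = 78% (1 - (2/3)(1/2) = 67%).
- I = 15: 1 - (1/3)(1/3) = 89% (1 - (1/3)(1/2) = 83%).

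For onset 0-15, no other single minute does better, because one reading can cover at most 10 of the 15 onset minutes.

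**Step 5. Fixed readings at 5, 15 and 25 minutes.** For d = 10 they record every onset from 0 to 25, so 100% (100%). For d = 5 they record onsets 0-5 and 10-15, so 10/15 = 67% (10/20 = 50%). With the routine cycle continuing, d = 5 becomes:
- I = 30: 1 - (1/3)(5/6) = 72% (1 - (1/2)(5/6) = 58%).
- I = 15: 1 - (1/3)(2/3) = 78% (1 - (1/2)(2/3) = 67%).

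| Schedule | d = 10, I = 30 | d = 10, I = 15 | d = 5, I = 30 | d = 5, I = 15 |
|---|---|---|---|---|
| Routine only | 33% | 67% | 17% | 33% |
| Plus check at a random minute | 56% | 78% | 31% | 44% |
| Plus check at minute 10 | 78% (67%) | 89% (83%) | - | - |
| Routine plus 5, 15, 25 | 100% | 100% | 72% (58%) | 78% (67%) |

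**Step 6. Longer falls.** A fall at least as long as the cycle is always charted. There is one qualification. On a 30-minute cycle alone, a 30-minute fall starting at minute s is first read after the window closes with chance s/30. Averaged over onsets 0-15, this is 7.5/30 = 25%. Such a fall is seen, but its first low reading may carry a time outside the window.

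**Step 7. Second dose.** At least 120/30 = 4 to 120/15 = 8 routine readings separate the doses.

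**The case against.** The best defense is that monitoring is specified, and that this is a wish for more detail. Section 5.3 requires readings before and after every dose in both arms, on top of a cycle that runs throughout enrollment. With a well-placed post-dose check, 78% to 89% of 10-minute falls starting in the first 15 minutes are already recorded. The documents do not show that brief, symptom-free falls below these thresholds occur at all: 1.2 reports no safety problems in the earlier labor trials, places 2 mg within the usual 1 to 3 mg dose, and says the protocol will comply with the labeling. Section 3.2 excludes women with heart rate below 70, systolic pressure below 90 or diastolic pressure below 50 on two sets of readings in the hour before study drug. A woman at 70 bpm would have to lose more than 20 bpm to count. Little formal use is made of the count either: there is no primary safety endpoint (6.5), neither event is a secondary endpoint (2.2.2), and even the lowest severity grade in 6.2.2 involves discomfort.

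Most of this stands, and it keeps the point small. It does not close the gap, because the favorable figures depend on a minute the protocol does not set. Local practice, or the DSMB document that 9.4.1 describes as attached, might be more specific. Neither is in the text available, so neither can be credited or criticized.

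A reader might infer more: that women go unwatched after dosing, that a second dose could be given to a woman with ongoing hypotension, or that the comparison between arms is biased. The documents support none of these. Readings after each dose are required. Four to eight routine readings precede any second dose, so only a fall that had already resolved could be overlooked. Monitoring is similar in both blinded arms, so the expected effect is under-counting in both.

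**Conclusion.** The concern holds in a limited form, and its severity is minor. The mismatch between a dose-timed event definition and a labor-timed measurement is plain from 5.3 and 6.2.1. Its size is not known: the 33% to 89% range for a 10-minute fall rests entirely on assumed fall length, onset and reading times. It describes how much the current wording leaves open and does not estimate how many events will be missed. Persistent bradycardia or hypotension, the hemodynamic concern that section 8 names, would be seen. Nothing here touches the cesarean comparison.

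**What to change.** In 5.3, define the monitoring around each dose as heart rate and blood pressure immediately before it and at 5, 15 and 25 minutes after it, in both arms, with the routine cycle continuing. The sponsor's clinicians should confirm the minutes. This places three readings inside the 6.2.1 window and uses a measurement the trial already takes. It improves the recording of 5-minute falls without making it complete.

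A reading before each dose is already required, so the added work is up to three cuff readings per dose: 326 x 3 = 978 at most for first doses, and 326 x 6 = 1,956 if every woman has both. Other costs are some nursing time, slightly more adverse events recorded, and a small departure from the statement in 3.4 that enrollment leaves routine labor care unchanged. Sample size, primary endpoint and analysis stay as they are.
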